Appendix A: BSI-18

Appendix B: BFI

Appendix C: BPI

Appendix D: Burden Interview

Appendix E: Demographic Form

Treatment Schema

	Pre-BMT	Day 0	Day 7¹	Day 30¹	Day 365²
Patient	BSI-18 BFI BPI	BSI-18 BFI BPI	BSI-18 BFI BPI	BSI-18 BFI BPI	BSI-18 BFI BPI
Caregiver	Demographics BSI-18 BFI Burden Interview	BSI-18 BFI Burden Interview	BSI-18 BFI Burden Interview	BSI-18 BFI Burden Interview	BSI-18 BFI Burden Interview

¹ Assessment can be done +/- 3 days

² Assessment can be done +/- 7 days

1.0 OBJECTIVES

Primary Objectives:

1.1 To investigate the level of distress and feelings of burden in caregivers of HSCT patients.

Secondary Objectives:

1.2 To investigate the impact of patient distress, fatigue and pain on the level of caregiver distress and burden.

1.3 To investigate the impact of caregiver distress and burden on overall patient survival and length of patient hospitalization.

1.4 To identify common characteristics of caregivers who report significantly more feelings of burden or distress.

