5.0 TREATMENT PLAN

Pre-BMT Patient Completes: BSI-18, BFI, BPI
Caregiver Completes: Demographic Form, BSI-18, BFI, Burden Interview

Days 0, 7, 30 and 365 Patient Completes: BSI-18, BFI, BPI
Caregiver Completes: BSI-18, BFI, Burden Interview

	Pre-BMT	Day 0	Day 7 ³	Day 30 ³	Day 365 ⁴
Demographics ¹	X				
BSI-18	X	X	X	X	X
BFI	X	X	X	X	X
BPI ²	X	X	X	X	X
Burden Interview ¹	X	X	X	X	X

¹caregiver only

²patient only

³assessment to be done +/- 3 days

⁴assessment to be done +/- 7 days

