6.0 ADVERSE EVENT REPORTING

Adverse events are further defined as “Any untoward medical occurrence in a patient or clinical investigation subject administered a pharmaceutical product and which does not necessarily have to have a causal relationship with this treatment.”¹⁵

Patients will be monitored by the investigators and data maintained by the Clinical Research Program. All Adverse Events will be graded with the Common Terminology Criteria for Adverse Events (CTCAE) Version 3.0.

http://ctep.cancer.gov/protocolDevelopment/electronic_applications/docs/ctcae3.pdf

Due to the non-treatment nature of this protocol, there are not expected to be any adverse events. However, should a patient experience an adverse event that is specifically related to participation in this study, the following reporting criteria will apply. Patients will be followed through Day 365 for protocol-related adverse events.

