8.0 STATISTICAL CONSIDERATIONS/DATA ANALYSIS

8.1 We will plan to accrue 50 autologous and 50 allogeneic patient/caregiver dyads. This number of patients will be sufficient to perform an initial analysis to examine levels of distress and associated outcome variables. We expect that patients will be accrued over 1-2 years.

8.2 Data analysis will be performed on the information gathered to evaluate the impact of HSCT on the caregiver's level of burden, depression, anxiety, somatic symptoms, fatigue and overall distress. It will also examine if caregiver burden leads to an increase in the patient's hospital utilization and overall outcome. In addition, we hope to identify these caregiver symptoms as they relate to the patient's overall functioning. The analysis will include t-tests to look at correlations, as well as more complex statistical procedures (e.g., manova, and multiple regression analyses) to identify relationships between variables.

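### For the survival part of objective 1.3, section 8.2 names methods that do not handle censored survival and fixes no exposure visit, which leaves open a burden score that depends partly on whether the patient survived

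*Combined protocol and SAP*

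**What the plan says.** Section 1.0 lists as secondary objective 1.3: "To investigate the impact of caregiver distress and burden on overall patient survival and length of patient hospitalization". Section 8.2 gives the question a causal direction: "It will also examine if caregiver burden leads to an increase in" the patient's hospital use and overall outcome.

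The exposure is measured repeatedly. In section 5.0 the Pre-BMT assessment is followed by "Days 0, 7, 30 and 365 Patient Completes" and, at the same visits, "Caregiver Completes: BSI-18, BFI, Burden Interview". That gives five visits. With the Burden Interview for burden and the BSI-18 for distress, there are 5 × 2 = 10 candidate exposure scores. The Day 365 form has a window of ± 7 days.

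On method, section 8.2 says "The analysis will include t-tests to look at correlations, as well as more complex statistical procedures", with MANOVA and multiple regression given as examples. It names no exposure visit, summary score, landmark or time-to-event method, and no other section supplies one. The documents do not say whether the caregiver continues to complete forms after the patient dies.

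On size, section 8.1 says "We will plan to accrue 50 autologous and 50 allogeneic patient/caregiver dyads", accrued over one to two years. The only stated follow-up limit concerns safety: "Patients will be followed through Day 365 for protocol-related adverse events".

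**The concern.** A claim that burden affects survival needs the burden score to come before the outcome. A Day 365 score mostly cannot. If the patient died in the first year, the form is either absent or completed in bereavement, except where it was completed between Day 358 and the death. A last, change, mean or maximum score that can draw on Day 365 therefore partly reflects whether the patient lived.

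If forms stop at death and the average score falls by Day 365, survivors look less burdened and burden appears harmful. If the average rises, burden appears protective. A maximum score leans towards protective even with no shift, because survivors contribute more forms.

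Two further features of section 8.2 add to this. The named methods take no account of time at risk. MANOVA over the five visits, in its usual complete-case form, would discard almost every patient who died in the first year, who are the patients that carry the information for this objective. The end of survival follow-up is also undefined, so with accrual over one to two years, follow-up could differ between dyads by about that much.

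**Working it through.** The plan gives no power, event or error figure for this objective, so there is nothing of its own to reproduce. What follows is illustrative.

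**From the documents:** 100 dyads (50 + 50); five visits; windows of ± 3 days at Days 7 and 30 and ± 7 days at Day 365.

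**Assumed:** one-year mortality 10, 20 or 30%; score SD 1; within-caregiver correlation 0.6; no true effect of burden on survival; 20% of deaths before Day 30 and the rest uniform to Day 365; forms stop at death; any mean shift occurs at Day 365 only; two-sided 5% test.

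**Step 1: deaths kept by a complete-case five-visit analysis.** The Day 365 form falls uniformly over 14 days (358 to 372). A first-year death is kept only if the form comes first. The chance per first-year death is 0.8 × (7²/2) / (14 × 335) = 0.8 × 24.5 / 4690 = 0.0042. Of 10, 20 and 30 deaths, the analysis keeps on average 0.04, 0.08 and 0.13. It keeps none with probability exp(−0.042), exp(−0.084) and exp(−0.125), that is 96, 92 and 88%. Simulation gave the same figures.

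**Step 2: false-positive rate, t-test by vital status.** The standard error of the difference is √(1/d + 1/(100 − d)) for d deaths: 0.333, 0.250 and 0.218. For a 0.5 SD shift:

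- Last score: the groups differ by 0.5, so z = 1.50, 2.00, 2.29 and the rejection rate is about 32, 52, 63%.
- Change from Pre-BMT: its SD is √(2 × 0.4) = 0.894, so z = 1.68, 2.24, 2.56 and the rate is about 39, 61, 73%.
- Mean of available scores: the groups differ by 0.5/5 = 0.1 and the survivors' SD is √(0.6 + 0.4/5) = 0.825, so z = 0.36, 0.49, 0.56 and the rate is about 7, 8, 9%.

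The simulation (4,000 runs per setting) agrees. Rates at 10/20/30% mortality, with ranges across mortality in the other columns:

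| Score | No shift | 0.2 SD either way | 0.5 SD lower | 0.5 SD higher |
|---|---|---|---|---|
| Last | 5% | 9–15% | 31/51/62% | 31/50/61% |
| Change | 5% | 9–18% | 38/59/71% | 38/58/71% |
| Mean of available | 5–6% | 5–6% | 7/8/9% | 7/8/9% |
| Maximum | 8–9% | 6–13% | 6/6/6% | 15/22/28% |

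**Step 3: variations.** A separate simulation with exponential survival, a Cox score test and mortality of 10 to 40% gave, for the mean score, 5 to 6% with no shift and 6.5 to 10.2% at 0.5 SD lower. Larger shifts matter more: 12 to 21% at 1 SD and 20 to 42% at 1.5 SD. If bereaved caregivers do complete forms, with scores raised by an assumed 1 SD, the mean score gave 13 to 28% with otherwise flat scores. Collecting forms after death therefore does not remove the problem.

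**Step 4: timing or method?** A Cox model on the last score gave 31/51/62% at 0.5 SD lower, the same as the t-test, so this inflation comes from timing. Pre-BMT, Day 0, Day 7, Day 33 landmark and time-updated scores all stayed at 4.2 to 5.8%.

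**Step 5: precision of the remedy.** The hazard ratio per SD detectable with 80% power is exp((1.96 + 0.84)/√deaths): exp(2.80/√10) = 2.4, exp(2.80/√20) = 1.9 and exp(2.80/√30) = 1.7.

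**The case against.** **The plan proposes no biased summary.** This stands. A reader might infer that the study will use Day 365 scores as the exposure, or that objective 1.3 carries a false-positive rate of 31 to 71%. The documents support neither. Those rates need a last or change score together with a 0.5 SD shift, and the plan states neither. For a mean score with shifts up to 0.5 SD, inflation is slight.

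**The list of methods is not closed.** MANOVA and regression are given as examples, so a survival method is not excluded. If every patient were followed to Day 365, a comparison by one-year vital status would involve no censoring. But no survival horizon is stated, and nothing in section 8.2 leads an analyst to a time-to-event method.

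**Deaths may be captured already.** Section 6.2 lists death as a serious adverse event, and section 6.1 sets reporting at one year after transplant. Against that, section 6.0 introduces the criteria for "an adverse event that is specifically related to participation in this study, the following reporting criteria will apply", which read literally leaves out transplant and disease deaths. Both readings are possible. It would go too far to say that deaths will not be recorded; the plan does not settle it.

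**Bereaved caregivers may not be assessed.** Section 4.2 requires the caregiver to be the primary caregiver of a transplant patient, which makes forms after death less natural but does not rule them out.

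**A landmark is not a cure.** This stands and limits the remedy. The 4.2 to 5.8% in step 4 assumes that death is independent of the scores, whereas objective 1.2 itself supposes that the patient's condition affects the caregiver. With no causal effect, a correlation of 0.2 to 0.4 between patient severity and the Day 30 score, a severity hazard ratio of 1.5 to 2.0 per SD and mortality of 10 to 30% (all assumed), a Day 30 landmark gave false-positive rates of 6 to 27%. Fixing the timing removes the dependence on survival, not confounding by the patient's condition.

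**Conclusion.** The concern holds as a specification gap with low severity. For the survival part of objective 1.3, section 8.2 names methods that do not handle censored survival, fixes no exposure visit, and leaves the end of survival follow-up undefined. Any exposure that includes Day 365 would depend partly on survival, and a complete-case five-visit analysis would keep fewer than one first-year death on average.

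How much bias results depends on mortality, score trajectory and choice of summary, none of which the documents give. It runs from about nil for last, change and mean scores with a flat trajectory to severe for a last or change score with a sizeable shift.

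The consequence is limited: 1.3 is secondary, section 8.1 calls the work an initial analysis, and primary objective 1.1 does not rely on this comparison.

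**What to change.** In section 8.2, state that:

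- The survival part of 1.3 uses Cox models from Day 0, one with the Pre-BMT Burden Interview score and one with the Pre-BMT BSI-18 score, each stratified by transplant type (autologous or allogeneic, the two accrual groups).
- Patients are censored at last contact or at the end of survival follow-up, with that end stated.
- Results are exploratory hazard ratios with confidence intervals.
- The Day 365 score enters no exposure for first-year survival.
- Later scores, if used, enter only through a Day 30 landmark (patients alive at Day 33, the end of the window) or as time-updated past scores. The result is described as an association, because patient condition may drive both burden and death. A sensitivity analysis may add the patient's BSI-18, BFI or BPI score from the same visit, as far as the number of deaths allows.

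Record dates of death and last contact, which the section 5.0 schedule does not list.

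**Cost.** A few sentences and two dates; no new visits or forms.

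**Downsides.**

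- Few deaths are likely, so estimates will be imprecise (step 5). If a fifth of deaths fall before Day 30, a landmark has 8, 16 or 24 deaths and detects hazard ratios of about 2.7, 2.0 and 1.8.
- Two unadjusted models give at least one p < 0.05 under no effect in about 8 to 10% of studies (score correlation 0.3 to 0.7 assumed), hence the exploratory label.
- The Pre-BMT score measures burden before transplant, not burden during it.

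Stratification is cheap protection if burden and mortality both differ by transplant type. With allogeneic caregivers assumed 0.5 SD higher and mortality of 5% (autologous) and 30% (allogeneic), the false-positive rate was 11.9% unstratified and 5.5% stratified. With mortality of 5% and 15% it was 6.1% and 4.8%.

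### Objective 1.3 and section 8.2 compare raw hospital days with no handling of death, so if mortality varies with caregiver burden the hospital-use result is distorted in a direction the documents cannot settle

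*Combined protocol and SAP*

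**What the plan says.** Section 1.0, secondary objective 1.3, relates the caregiver's distress and burden to "overall patient survival and length of patient hospitalization". The two outcomes stand side by side and neither is defined.

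Section 8.2 gives the direction of interest: "It will also examine if caregiver burden leads to an increase in the patient's hospital utilization and overall outcome". More hospital use is the harmful direction, so fewer days reads as better. On methods it says: "The analysis will include t-tests to look at correlations, as well as more complex statistical procedures (e.g., manova, and multiple regression analyses". It names no time-to-event, competing-risk, rate or composite method.

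Section 8.1 sets the size: "We will plan to accrue 50 autologous and 50 allogeneic patient/caregiver dyads". The justification is verbal: "This number of patients will be sufficient to perform an initial analysis to examine levels of distress and associated outcome variables".

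Section 6.0 states: "Patients will be followed through Day 365 for protocol-related adverse events". That fixes a horizon for adverse events, and the last questionnaire is also at Day 365, but no window is given for counting hospital days. Apart from objective 1.3, death appears only as a serious adverse event category in section 6.2.

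**The concern.** A patient who dies in hospital on Day 20 can contribute at most about 20 post-transplant hospital days and can never be readmitted. A patient who recovers after a 25-day stay contributes 25. With no rule for death, a t-test or regression on raw days takes the first value as an ordinary low one, and so as the better result.

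This matters most if the study's own hypothesis is true. If the patients of burdened caregivers both die more often and use more hospital care, the hospitalization analysis mixes the two effects. The study could then report a weak, absent or protective association where both components are harmful. Objective 1.3 is the only objective about patient outcomes, and the background section repeats it as part of the study's purpose.

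**Working it through.** The plan has no figure to reproduce: it gives no death rate, mean stay, SD, alpha, power or effect size. Every input below is an assumption except the 100 dyads (50 + 50) from section 8.1.

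**1. Total days to Day 365, two groups, by hand.** Patients spend 60% of the first 30 days and 3% of later days in hospital while alive.
- Survivor: 0.6 × 30 + 0.03 × 335 = 28.05 days.
- Death spread evenly over Days 5 to 100: (25 × 10.5 + 70 × 19.05) / 95 = 16.8 days.
- Low burden, 10% mortality: 0.9 × 28.05 + 0.1 × 16.8 = 26.9.
- High burden, in-hospital rate 10% higher. If nobody died the difference would be 0.1 × 28.05 = +2.8.

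| High-burden mortality | High-burden mean | Naive difference |
|---|---|---|
| 20% | 1.1 × 25.80 = 28.4 | +1.5 |
| 30% | 1.1 × 24.675 = 27.1 | +0.2 |
| 40% | 1.1 × 23.55 = 25.9 | -1.0 |

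With no effect on the rate and 30% v 10% mortality, the difference is 24.675 - 26.925 = -2.3 days, a spurious protective result.

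**2. Index stay.** With constant hazards, mean stay = 1 / (discharge hazard + death hazard). Mean times to discharge without death are 20 and 22 days (true difference +2.0).
- Equal death hazards (0.002): 1/0.0520 = 19.2 v 1/0.0475 = 21.1, difference +1.8.
- In-hospital death 3.8% v 15% (hazards 0.002 and 0.008): 19.2 v 1/0.0535 = 18.7, difference -0.5.

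**3. Slope per SD of burden (simulation).** Burden is standardized and survival is exponential with hazard ratio 1.5 per SD. Hospital days accrue while alive at 0.6 per day to Day 30 and 0.06 per day after, so a full year gives 18 + 20.1 = 38.1 days. A 5% effect per SD is then a true slope of about +1.9.

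| One-year mortality | 10% | 20% | 30% |
|---|---|---|---|
| No effect on hospital use | -0.5 | -0.9 | -1.3 |
| Same, last 15 days before death all inpatient | 0.0 | 0.0 | -0.1 |
| Same, last 20 days all inpatient | +0.2 | +0.3 | +0.3 |
| 5% effect (true +1.9), no terminal stay | +1.3 | +0.8 | +0.3 |

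With hazard ratio 1.0 and the 5% effect, the slope is +1.8 to +1.7, so little is lost.

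**4. Inflation.** In the setting of step 1 with rate ratio 1.1 and 30% v 10% mortality, put deaths between Days 30 and 365 and add 20 inpatient days before each. The naive difference becomes +5.6 against +2.8 if nobody died.

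**5. Against the study's precision.** If the SD of hospital days is 15 to 20 (assumption), the standard error of a slope per SD of burden is about SD/√100 = 1.5 to 2.0 days. The spurious slope of -1.3 is below that. The largest shortfall, 1.9 - 0.3 = 1.6, is about one standard error.

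**The case against.** The strongest objection concerns direction. A reader might infer that death always biases the result against the hypothesis in 8.2. The documents do not support that. They say nothing about inpatient time before death, and step 3 shows that 15 to 20 terminal days remove or flip the bias. This objection stands: the sign is unknown.

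A reader might also infer that a truly harmful association would be reversed. None of the slope scenarios does this; they attenuate. Reversal appeared only with wide mortality gaps (40% v 10% in step 1, 15% v 3.8% in step 2).

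Nor do the documents state that a death is scored as a short stay. That follows from the absence of a rule together with the methods named.

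Survival is reported under the same objective, so excess deaths would be visible. This helps interpretation but does not correct the hospital-day estimate or show how much of it death produced.

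Length of hospitalization may mean only the index stay. The year-long calculation and the readmission argument would then not apply, although step 2 shows the same mechanism. The missing definition is therefore part of the problem.

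Finally, days alive and out of hospital looks like a natural replacement, but it would answer a different question. In the step 3 model without terminal stays it gives about -6.6, -13.3 and -19.5 days per SD with no effect on hospital use, against -8.4, -14.8 and -21.4 with the 5% effect, so roughly 80% to 90% of it is mortality. It would still show harm (about -3 to -16) if burden lowered hospital use by 10% per SD.

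**Conclusion.** The concern holds in a limited form. As written, the plan compares hospital days separately from survival with no handling of death, and the result is distorted if mortality varies with burden. The distortion may mask, attenuate, create a spurious protective association, or inflate; the documents fix neither its sign nor its size. Under a hazard ratio of 1.5 per SD and 10% to 30% one-year mortality it is about -0.5 to -1.3 days per SD without terminal stays and about 0 to +0.3 with 15 to 20 terminal inpatient days. It is negligible if burden and mortality are unrelated. For 100 dyads this is probably within one standard error, given an assumed SD of 15 to 20 days. The objective is secondary and the primary objective is unaffected. The change is worth making because it is cheap and the raw comparison cannot be interpreted without it.

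**What to change.** In 1.3 and 8.2:

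- Use one hospital-use outcome under one name, with a stated window (for example Day 0 to Day 365), and say whether it is the index stay or all inpatient days.
- Analyse it in a way that accounts for death. For the index stay, use time to discharge with death as a competing event. For the whole window, use hospital days per day alive. Estimate that rate separately for the early and later periods, because hospital use is concentrated early: under the step 3 inputs a death at Day 20 gives 12/20 = 0.60 and a one-year survivor 38.1/365 = 0.10.
- Add days alive and out of hospital to Day 365, counting days after death as zero, as a companion outcome and not a replacement.
- Show survival and raw hospital days by vital status at Day 365 beside it.

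Cost: a wording change and a little more analysis. It needs only admission, discharge and death dates, which objective 1.3 already requires. The companion outcome is driven mostly by mortality, so it must not be reported without its components.

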2.0 BACKGROUND

Hematopoietic stem cell transplant (HSCT) is an established treatment for certain hematologic malignancies¹. The process of undergoing HSCT is intense and time consuming. Patients and their caregivers are required to commit to several months of treatment and close follow-up. At our institution, the Blood and Marrow Transplant Program at Northside Hospital, the transplant process includes frequent, if not daily, visits to the clinic, and at times lengthy hospital stays for the patient. Our program requires patients to have a full-time caregiver to assist them with transportation, treatment compliance, nutritional intake and emotional support. Patients are not allowed to be alone, go to public areas, or independently manage their medications. Patients are most commonly out of work for extended periods of time. The need for a caregiver places an extra burden on the patient and their loved ones, as caregivers are not able to work full time while caring for an HSCT patient. Many studies have looked at the quality of life and various psychological symptoms in patients undergoing HSCT. Studies have analyzed the impact of HSCT on patient health related quality of life (HRQOL) during and after HSCT. However, little is known about the impact of HSCT on spouses/partners or other primary caregivers.

The process of serving as a caregiver for a loved one going through HSCT is rigorous and stressful. Much of the psychosocial support that exists in transplant centers focuses on the patients with little support for the caregivers. Friends and family also tend to place emphasis on the patient undergoing the treatment and give less attention to the patient's caregiver. Even with the presence of community support groups and education from the transplant programs, caregivers typically report experiencing high levels of distress. Caregivers often express feeling the weight of the world on them, as they are left to worry about everything outside of transplant (i.e. finances, child care), in addition to being very concerned with the patient's health. They feel a sense of responsibility for the patient improving medically.

More recently, transplant programs have begun to identify needs of HSCT caregivers. Researchers have begun to recognize caregivers as an important and often overlooked participant

in the HSCT process. The current literature on HSCT caregivers suggests that caregivers for HSCT patients do report feeling stressed, exhausted emotionally and physically, and in need of support^{2,3,4}. One study identified high levels of stress and depression pre-transplant⁵. A 2004 study by Gaston-Johansson⁶ found that primary caregivers of patients with breast cancer scheduled for BMT experience fatigue, anxiety, burden of care, and low quality of life.

Due to these previous findings, it was clear that level of burden, fatigue and distress were essential properties to be measured in HSCT caregivers. Each of these areas will be measured by a specific, psychometrically sound instrument. The Burden Interview, The Brief Fatigue Inventory, The Brief Pain Inventory and the Brief Symptom Inventory-18^{7, 8, 9, 10, 11, 12, 13, 14} were selected due to their previous use in oncology settings.

The purpose of this study is to examine the impact of HSCT on the caregiver's level of burden, depression, anxiety, somatic symptoms, fatigue and overall distress. It will also examine if caregiver burden leads to an increase in the patient's hospital utilization and overall outcome. In addition, we hope to identify these caregiver symptoms as they relate to the patient's overall functioning. Therefore, each patient will also complete self-report measures in order to assess if the patient's level of distress impacts the caregivers' functioning. The patients will complete self-report measures assessing symptoms of psychological distress, pain and fatigue and these scores will be matched to their particular caregiver.

